Pre-screening. All interested individuals will undergo a pre-screening process, conducted via phone or in-person by a study RA, student intern, or other trained study team member, to evaluate preliminary eligibility. A Pre-Screen ID number will be assigned to each individual during this process. Data collected during pre-screening will be recorded in a password-protected spreadsheet or within REDCap hosted at TFI.

Informed Consent. Individuals who meet pre-screening criteria will be scheduled for a Screening Visit (Visit 1), where we will conduct the informed consent discussion and obtain written consent. A trained study RA will review the consent form with the individual in detail, discuss the overall goals of the study, and review all procedures. Individuals will be asked to voice their understanding of the information and will have adequate time to ask questions. If they agree to participate, they will be asked to sign the informed consent form and will be provided with a copy for their records. Informed consent discussions will take place in private consult rooms at TFI.

Inclusion Criteria		Exclusion Criteria	
1)	Age 18 or older	1)	Not English-speaking
2)	Living with HIV	2)	Unwilling to interact with the TruTag app
3)	Currently prescribed and taking Biktarvy as ART for at least 3 months		
4)	Undetectable viral load in prior 6 months		
5)	Owns iPhone model 11 or higher (non-SE only)		

5. Participant Enrollment.

Once the informed consent form and Medical Release Form have been signed, study staff will confirm eligibility. Individuals will be asked to provide their most recent viral load results to confirm undetectable viral load during the prior 6 months. If they do not have recent viral load results, study staff will obtain an HIV viral load during this visit, or, if preferred, individuals can obtain a viral load from their HIV care provider. Individuals who meet all criteria will be scheduled for an Enrollment Visit (Visit 2).

6. Study Procedures.

Study Visits. There are a total of five visits during the study period: the Screening Visit (Visit 1), Enrollment Visit (Visit 2), Month 1 Visit (Visit 3), Month 2 Visit (Visit 4), and Month 3 Visit (Visit 5).

[figure not shown]

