Screening Visit (Visit 1): As described above, potential participants will be approached and prescreened, either via phone or email, by a trained member of the study team. Individuals who meet the pre-screening criteria will be scheduled to attend an initial Screening Visit (Visit 1), where the informed consent process will be conducted and study eligibility will be confirmed. Following the consent process, individuals will be asked to sign a Medical Release Form and Locator Form. A Screen ID number will be assigned at this visit. Study staff will confirm that individuals have been diagnosed with HIV, have been taking Biktarvy for at least 3 months prior to the Screening Visit, and have an undetectable viral load documented within the past 6 months. Study staff will administer a blood draw for DBS testing, in order to measure baseline ART adherence. All individuals will be enrolled in the ClinCard remuneration system during this visit, and study staff will issue payment following completion of visit procedures. Following this visit, if eligibility has been confirmed, we will notify the Fenway Pharmacy and schedule participants for the Enrollment Visit (Visit 2).

Enrollment Visit (Visit 2): At the Enrollment Visit (Visit 2), participants will be formally enrolled in the study. Participants will complete a baseline quantitative assessment (e.g., sociodemographics, sexual history, attitudes about technology). Participants will be informed that they may skip any questions they do not feel comfortable answering. The study team will introduce participants to the TruTag technology via a brief PowerPoint presentation, which will cover its functionality and structure, and provide answers to common questions. Participants will receive a standardized training on operation of the TruTag system, and will be assisted with downloading the TruTag app onto their phone. We will assist participants in registering the app, and we will program in standardized reminders (see *In-Study Messaging* section). Study staff will bring a completed Prescription Card to the Fenway Pharmacy, which will dispense 30 ART pills for the first month of the study. Participants will be provided with the 30-day supply of pills and will be instructed to take one pill once daily. Their first dose will be observed by the study team during this visit. We will then issue a ClinCard payment and schedule the Month 1 Visit (Visit 3).

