Remuneration. Participants will be remunerated a total of \$275 via the ClinCard system, according to the following payment schedule, upon completion of all study visit procedures.

Study Visit	Compensation
Screening Visit (Visit 1)	\$40
Enrollment Visit (Visit 2)	\$40
Month 1 Visit (Visit 3)	\$65
Month 2 Visit (Visit 4)	\$65
Month 3 Visit (Visit 5)	\$65
Total	\$275

TruTag System. The TruTag system leverages a silica-based FDA generally regarded as safe (GRAS) microparticle that is incorporated into the coating of B/F/TAF. When light shines from a smartphone camera onto the coated drug, the reflected optical image is interpreted as B/F/TAF. A corresponding app records each scan as an adherence event and patients using the TruTag system are coached to scan their medication prior to ingesting it. Dissolution of B/F/TAF when overcoated with the TruTag system was tested by Gilead Sciences, demonstrating that there is no change in dissolution. Specialty coated B/F/TAF will be provided through a cooperative agreement between Gilead Sciences and TruTag. In brief, B/F/TAF from the Gilead manufacturing supply chain will be overcoated with the TruTag system by ThermoFisher, the Gilead contract coating manufacturer. Drug will then be shipped in bottles of 30 to the Fenway Health Pharmacy.

In addition to recording adherence events, the TruTag app also provides a calendar for participants to review their adherence on-demand, as well as reminder systems that are triggered if no adherence event is detected by the TruTag system during a 24-hour period. Finally, the app

provides a secure platform to facilitate two-way text message communication between participants and the study team. This platform will be used to provide study-related reminders and communication in the setting of detected nonadherence.

In-Study Messaging. Participants will receive communications via the TruTag app during their participation in the study. Messaging will include: (1) daily adherence reminders, (2) reminders following detected nonadherence, (3) study-related reminders of upcoming visits, and (4) responses to technology-related questions.

Daily Adherence Reminders. During installation of the TruTag app, study staff will ask participants what time of day they expect to take their daily B/F/TAF dose. We will set up daily adherence reminders in the app for 10 minutes prior to their expected dosing period.

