Data Collection. Quantitative data will be collected via the baseline quantitative assessment at the Enrollment Visit (Visit 2), and via the System Usability Scale at the Month 3 Visit (Visit 5). Study staff will collect participant monthly adherence via the TruTag application and create timeline followback discussions at the Month 1 Visit (Visit 3), Month 2 Visit (Visit 4), and Month 3 Visit (Visit 5) to identify and contextualize adherence events of interest across the study period. Qualitative data will be collected via individual qualitative interviews at the Month 3 Visit (Visit 5). Dried blood spot testing will be conducted at the Screening Visit (Visit 1) and the Month 3 Visit (Visit 5). Lastly, general participant TruTag application usage will be collected to better understand participant engagement with the application. This will include: app engagement, including time spent in the app and which screens of the application participants access along with the frequency and time in which they spend on each screen on the application, as well as reminder data, including number of reminders delivered, timing of reminders, dosing window around which reminders will be sent, and conversion rate (days in which a reminder is delivered and adherence event recorded afterwards in the TruTag appl.

Baseline Quantitative Assessment. Quantitative data, including questions related to sociodemographics, use of ART, sexual history, mental health, attitudes about technology, medical mistrust, and substance use will be collected via a quantitative assessment. Quantitative data will be stored and managed on the REDCap platform hosted at TFI.

System Usability Scale. Participants will complete the System Usability Scale (SUS)¹¹ at the Month 3 Visit (Visit 5). The SUS is a 10-item Likert scale which will assess participants' perceptions of the usability of TruTag technology.

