Risks of Psychological Discomfort while Completing Assessments. Study questionnaires and interviews may include questions that individuals do not feel comfortable answering, or that may cause psychological discomfort. Individuals will be informed during the consent process that they may choose to skip any questions that they do not want to answer. They will also be reminded that they may withdraw from the study at any time, for any reason, without penalty.

Risks of Blood Draws. Participants will be informed during the consent process that they may have a bruise or pain from the site where blood samples are drawn. There is also a small risk of infection, lightheadedness, and/or fainting. To mitigate this risk, all study staff will be trained in phlebotomy at Fenway Health. We will ask participants who have a history of vasovagal syncope from blood draws to lie flat or sit in a recliner prior to blood draw. We will also have oral fluids available for participants at visits where blood draws are required.

8. Benefits.

Individuals may not benefit directly from participation in this study. They may indirectly benefit from learning about the TruTag system as a tool for measuring their ART adherence behaviors.

9. Statistical Analysis.

We will calculate basic descriptive statistics for key demographic variables. SUS scores will be summed and a mean score will be calculated for each participant. Overall SUS will be measured at each month during study participation. We will measure adherence via three strategies: (1) TruTag recorded adherence, (2) pill count at each monthly study visit, and (3) dried blood spot tenofovir alafenamide concentration. Correlation coefficients will be calculated between each of these adherence metrics. To measure if correlation of measures degrades over time (e.g., if individuals disengage from the TruTag system and stop using it over time), we will use a point biserial correlation.

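### Section 9 tests whether the correlation between adherence measures degrades over time with a point-biserial correlation, but names neither its variables nor its time unit; applied to the scan record, it measures change in scanning, not change in correlation.

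*Combined protocol and SAP*

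**What the plan says.** Section 9 lists three adherence measures: the TruTag record, a pill count at each monthly visit, and a DBS drug concentration. It then says: "Correlation coefficients will be calculated between each of these adherence metrics". The type of coefficient and the time window are not given. The next sentence sets the question, "To measure if correlation of measures degrades over time", gives disengagement from TruTag as the example, and names the method: "stop using it over time), we will use a point biserial correlation". No section says which variable is binary, which is continuous, or what the unit of time is.

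Three other places matter:

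- Section 6, TruTag System: "A corresponding app records each scan as an adherence event". The record is therefore of scans, not of ingestion.
- Section 6, Screening Visit: "Study staff will administer a blood draw for DBS testing, in order to measure baseline ART adherence". The app is installed later, at the Enrollment Visit. Section 6, Data Collection, gives the only other DBS time as Month 3.
- Section 6, Study Outcomes: correlating TruTag with traditional adherence measures is the secondary outcome.

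**The concern.** A point-biserial coefficient is the Pearson correlation of one binary with one continuous variable. With period as the binary variable, it is a rescaled difference in means. The stated question is different: whether the association between two measures, in the same people, changes across three months. All three adherence measures are quantitative and there are three monthly visits, so an analyst must invent the pairing. Two analysts following the same plan could report different quantities.

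At stake is the one sentence in Section 9 on whether TruTag keeps tracking pill-taking through the 90 days. If the coefficient is computed on the scan record, a fall in scanning looks the same whether TruTag has lost track of pill-taking or is recording missed pills correctly. Participants and data collection are not affected.

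**Working it through.** The plan gives no expected correlation, power or precision for this analysis, so there is no figure of its own to reproduce. The check asks what each possible coefficient estimates.

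**Inputs.** From the plan: n = 15, monthly TruTag/pill-count pairs, DBS at Screening and Month 3. Assumed, not trial data: adherence mean 92%, SD 5 (variance 25); scan-recording noise SD 2 (variance 4); 3 points of constant under-recording; 5 of 15 people affected at Month 3, each losing 30 to 90 points (uniform: mean 60, variance 60²/12 = 300).

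**Spread of the loss over all 15.** Mean = (5/15) × 60 = 20. Variance = (5/15)(60² + 300) − 20² = 1,300 − 400 = 900.

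**Month 1.** Pill-count variance 25, scan variance 25 + 4 = 29, covariance 25. Correlation = 25/√(25 × 29) = 0.93.

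**Case A, five people stop scanning but take their pills.** Month 3 pill-count variance 25, scan variance 25 + 4 + 900 = 929, covariance 25. Correlation = 25/√(25 × 929) = 0.16.

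**Case B, the same five miss pills and scans follow.** Pill-count variance 925, scan variance 929, covariance 925. Correlation = 925/√(925 × 929) = 1.00.

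**Point-biserial of month with scans.** For two equal groups it is (M3 − M1)/(2s), where s² is the mean within-month variance plus the square of half the mean difference. In both cases s² = (29 + 929)/2 + 10² = 579 and s = 24.06, so the coefficient is −20/48.12 = −0.42.

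**Month with the signed gap (TruTag minus pill count).** Case A: s² = (4 + 904)/2 + 10² = 554 and s = 23.54, giving −20/47.08 = −0.42. Case B: the mean gap does not move, giving 0.

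**Case C, association lost with equal means.** M3 − M1 = 0 for scans and for the signed gap, so both coefficients are 0 while the correlation goes from 0.93 to 0.

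Simulation medians with values capped at 0–100% agree:

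| Quantity | A: scans missed | B: pills missed | C: association lost |
|---|---|---|---|
| TruTag/pill-count Pearson, Month 1 to 3 | 0.93 to 0.15 | 0.93 to 1.00 | 0.93 to 0.00 |
| Month with scans | −0.42 | −0.42 | 0.00 |
| Month with signed gap | −0.43 | 0.00 | 0.00 |
| Month with absolute gap | 0.43 | 0.00 | 0.39 |
| Monthly point-biserial, median-split TruTag with pill count | 0.75 to 0.44 | 0.75 to 0.69 | 0.75 to 0.01 |

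Daily scan/no-scan against study day, with five people stopping on a random day from 31 to 90, gives −0.24 in both A and B.

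**Sensitivity.** With 3 to 7 people affected, adherence SD 5–15 and noise SD 2–5, month with scans runs from −0.28 to −0.52 and is equal within each A/B pair. Month 3 Spearman is 0.30–0.61 in A and 0.91–0.99 in B.

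**DBS.** The Screening sample precedes any TruTag use, so there is one on-study TruTag/DBS pairing, at Month 3, and no change over time can be formed from it.

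**The case against.** The strongest reply is that the plan under-specifies the method rather than choosing one that cannot work. This stands. Dichotomising TruTag, computing a point-biserial with pill count each month and comparing months separates all three cases in the table. Month with the absolute gap also responds to lost association, and month with the signed gap picks out the plan's own disengagement example. A reader might infer that a point-biserial correlation can never answer the question; the documents do not support that. But Section 9 states none of these constructions. Dichotomising discards information that the plan collects. The absolute gap measures agreement rather than correlation: in a separate check with the correlation held at 0.7 and the TruTag mean falling by 1 SD, it still gave 0.37.

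A reader might also infer that the trial could not tell missed scans from missed pills. That goes too far. The preceding sentence permits monthly TruTag/pill-count correlations, which would show 0.15 against 1.00 at Month 3 in the example. Timeline followback and staff contact after 48 hours gather reasons for missed scans. However, Section 9 neither requires the correlations by month nor brings those reasons into this analysis.

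Finally, the equal −0.42 values follow from taking the same loss off the scan record in both cases. That is so, and it is the point: a coefficient computed from scans alone cannot see the difference.

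**Conclusion.** The concern holds in this form: the variables and time unit are not named, and a single point-biserial of month or study day with the scan record measures change in scanning, not change in correlation. The signed-gap version separates missed scans from missed pills but stays near 0 if association is lost with equal means. Constructions that would respond exist but are not specified. The sizes (−0.42 in both cases, against Month 3 correlations of 0.15 and 1.00) rest on assumed inputs. That a scan-only coefficient is blind to pill-taking does not depend on them.

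The point is minor. It concerns a secondary, exploratory analysis in 15 people, and the primary feasibility and acceptability outcomes do not depend on it.

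**What to change.** Replace the point-biserial sentence in Section 9 with:

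> For each month we will report the TruTag/pill-count correlation (Pearson and Spearman) with a participant-bootstrap 95% CI, and the Month 3 minus Month 1 change; the mean signed and mean absolute TruTag-minus-pill-count difference by month, with the within-participant Month 3 minus Month 1 change and 95% CI; and a listing or plot of each participant's monthly values. Correlations in months without variation will be reported as not estimable. TruTag will be compared with DBS at Month 3 only. These are exploratory estimates.

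**Why both coefficients.** Pearson reacts more to a few people who stop scanning (Month 3 value 0.15, against 0.43 for Spearman in the five-person example); Spearman depends less on extreme values.

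**Why the not-estimable clause.** Entry requires "Undetectable viral load in prior 6 months", so adherence may be near its ceiling. If all 15 had the same true daily adherence p (assumed), the chance that nobody misses a pill in 30 days is p^(15 × 30): 1% at 99%, 10% at 99.5% and 41% at 99.8%.

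**Cost.** Wording and slightly more analysis; no new data. Pill counts may be late or missing when Month 1 and Month 2 visits are held by Zoom, and should be counted as missing by month.

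**Precision is low.**

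- For a true fall from 0.8 to 0.5, the bootstrap interval for the change excludes zero in about 30–48% of simulated trials with Pearson and 17–20% with Spearman.
- The half-width for the mean signed-gap change is 2.145 × SD/√15. With SD about 31, as in the five-person example, it is 17 points around −20.
- With three people stopping, the result is about −12 ± 14, which includes zero. The participant listing is therefore needed alongside the means.
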